- [REDACTED]
- [REDACTED]

Required Observations:

[REDACTED]

Day of Graft Infusion: [REDACTED]

[REDACTED]

Post-HSCT: [REDACTED]

[REDACTED]

V. EVALUATION CRITERIA

Primary Endpoint:

The primary endpoint of the study is safety of infusion of TCR $\alpha\beta$ +/CD19+ depleted donor grafts.

We will determine the frequency and characteristics of potential infusion-related toxicity. Experience at our center using CD34+ selected stem cells has shown infusion related toxicity occurs at an incidence of <5%. We previously observed zero infusion reactions in 22 patients who received a CD34+ selected boost product as part of a CCHMC study (IRB# 2010-2344), and 2 infusion reactions among 55 infusions which were performed as part of clinical care including 1 occurrence of hypertension, and 1 occurrence of urticaria that resolved with anti-histamine administration. While there is little expectation of infusion-related toxicity, the incidence of infusion-related reactions will be recorded and evaluated.

Secondary Endpoints:

The secondary endpoints of the study are to assess engraftment and acute GVHD incidence.

Engraftment:

Engraftment and graft function are monitored on a clinical basis. Neutrophil recovery will be defined as the first of 3 consecutive days that the absolute neutrophil count is 500 cells/mcL. Platelet recovery will be defined as the first of 3 consecutive days that the platelet count is greater than 20 without any platelet cell transfusions in the previous 7 days. Initial donor-derived hematopoietic cell recovery will be defined as having 95% or greater donor-derived cells. Initial mixed donor and recipient-derived engraftment will be defined as having less

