We will report the Day +100 event-free survival of patients where an event is defined as death, primary graft failure, autologous recovery (<5% donor-derived cells in whole blood or in the cellular compartment of interest, i.e. T cells in patients with SCID), secondary graft failure, receipt of an additional hematopoietic cell

product other than for control of infection (Donor lymphocyte infusion or Virus-Specific T cell infusion), and second allogeneic HSCT.

Acute GVHD:

Clinical assessments for acute GVHD are frequently performed using Modified Glucksberg Criteria as in Appendix 1. We will collect clinical information regarding incidence and severity of acute GVHD. We will report the Day +100 cumulative incidences of acute GVHD grades II-IV and III-IV.

Chronic GVHD:

Clinical assessments for chronic GVHD are also frequently performed using NIH Consensus criteria. We will report the 1 year cumulative incidences of chronic GVHD.

GVHD-Free Survival:

Based on the presence or not of acute or chronic GVHD at 1 year, we will report GVHD-free survival at 1 year.

VI. OFF STUDY CRITERIA/CRITERIA FOR WITHDRAWING SUBJECTS

Subjects (or parents or legal guardians) have the right to withdraw from the study at any time and for any reason without prejudice to his or her future medical care by the physician or the institution.

Any subject who withdraws consent to participate in the study will be removed from further treatment and/or study observation immediately upon the date of request. The subject will be followed for safety purposes for at least 1 week after infusion of the stem cell product.

Criteria for Removal from Protocol Therapy:

- Patient withdrawal from protocol therapy

Off Study Criteria:

- a) Death
- b) Receipt of a second stem cell product
- c) Lost to follow-up

VII. STATISTICAL CONSIDERATIONS

1. Sample Size and Study Duration:

We chose a sample size of 80 patients based on estimates of patient need for access to T cell depleted grafts over 3-5 years at our Institution. All patients will be followed for primary and secondary endpoints for at least 100 Days following allogeneic HSCT, and 1 year data will be collected regarding survival and presence or absence of acute or chronic GVHD.

2. Statistical Considerations for Data Analysis:

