Data will be presented with descriptive statistics. Cumulative incidence curves will be created to analyze engraftment and acute GVHD. Death will be treated as a competing event. Probability of overall survival and event-free survival will be estimated with Kaplan-Meier curves.

3. Stopping Rules:

A predictive probability design (Lee, Lin. Clinical Trials. 2008) will be used to control for safety with respect to TRM. The unacceptable rate of TRM is 30% or more. This will be tested against a one-sided alternative. The trial will initialize by enrolling 10 patients. If 3 or more out of 10 have a TRM the trial will stop.

Otherwise the trial will continue according to the stopping rules plan (Appendix 2) up to a maximum of 73 patients. If the number of patients with a TRM within 100 days following allogeneic HCT is ever greater than or equal to the number listed in the corresponding patients enrolled row the trial will stop and the drug will be declared not safe. This design yields a type I error rate 0.05 and power greater than 80% when the true rate of TRM is 15%. Note the stopping rule must be made based on the chronological order of the patients enrolled.

We plan to meet with medical monitor approximately every quarter to review these safety data and stopping rules. The medical monitor will review the TRM data in the context of HLA mismatch; and as usual, he/she will have the final authority regarding continuation of the study in the event of excessive TRM.

VIII. REGULATORY, ETHICAL, AND STUDY OVERSIGHT CONSIDERATIONS

The protocol and informed consent document for this study must be approved in writing by the Institutional Review Board (IRB) prior to any patient being registered on the study.

Changes to the protocol must also be approved by the IRB. Records of the Institutional Review Board review and approval of all documents pertaining to this study must be kept on file by the investigator and are subject to FDA inspection at any time during the study. Periodic status reports will be submitted to the Institutional Review Board at least yearly, as well as notification of completion of the study and a final report within 6-12 months of study completion or termination. Informed consent will be obtained prior to the treatment of participants.

1. Data Safety Monitoring Plan:

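### One-year GVHD-free survival is defined by GVHD status at 1 year, so GVHD that occurred and resolved earlier counts as GVHD-free

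*Combined protocol and SAP*

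**What the plan says.** Section I (Secondary Objectives) names 1-year GVHD-free survival without defining it. The definition is one sentence in section V, GVHD-Free Survival: "Based on the presence or not of acute or chronic GVHD at 1 year, we will report GVHD-free survival at 1 year". Section VII.1 describes the matching data: "1 year data will be collected regarding survival and presence or absence of acute or chronic GVHD".

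The two entries just before it in section V are worded differently. For acute GVHD: "We will report the Day +100 cumulative incidences of acute GVHD grades II-IV and III-IV". For chronic GVHD: "We will report the 1 year cumulative incidences of chronic GVHD". Day +100 event-free survival, also in section V, has an itemised list of events.

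On analysis, section VII.2 says "Probability of overall survival and event-free survival will be estimated with Kaplan-Meier curves" and, more generally, "Data will be presented with descriptive statistics". GVHD-free survival is not named there. The opening summary of secondary endpoints in section V omits it too: "The secondary endpoints of the study are to assess engraftment and acute GVHD incidence".

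**The concern.** The hypothesis in the Abstract is that the graft limits grade II-IV acute GVHD. A GVHD-free survival figure should therefore fall when a patient has such an episode. Under a status rule it falls only if the GVHD is still present at 1 year. Acute GVHD that was treated and settled leaves no trace in the composite, and neither does chronic GVHD that resolved within the year. A reader of the final report would probably take the figure as the share of patients who passed the first year alive and without GVHD, and it would be too high for that use. The composite also cannot be rebuilt from the separately reported incidences, because they do not show which patients had both forms or died.

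**Working it through.** The plan states no rate, target, test or precision for this endpoint, so there is no figure to reproduce. The check is a comparison of the text, followed by a look at what Table 1 can say about size.

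**Step 1: how each history is scored**

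| Patient history | Status at 1 year (as written) | First event by 1 year | Other stated endpoint that captures it |
|---|---|---|---|
| Grade II-IV acute GVHD before Day +100, resolved, alive | GVHD-free | Failure, if that grade counts | Day +100 acute GVHD incidence |
| Acute GVHD starting after Day +100, resolved, alive | GVHD-free | Failure, if that grade counts | None stated |
| Chronic GVHD resolved before 1 year, alive | GVHD-free | Failure | 1-year chronic GVHD incidence |
| Death without GVHD | Failure (implied by the word survival) | Failure | Overall survival |
| Grade I acute GVHD present at 1 year | Failure (no grade is stated) | Depends on the chosen grade | None stated, if it starts after Day +100 |

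The second row has no other endpoint because section X.8 describes follow-up for acute GVHD through Day +100.

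**Step 2: direction.** With the same grade threshold in both rules, every first-event success is also a status success, so the status figure can never be the lower one. The gap is the proportion of patients who had GVHD earlier and are alive and GVHD-free at 1 year. If the thresholds differ, the last row can pull the other way, so the status figure is usually, not always, the higher one.

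**Step 3: what Table 1 (section III) offers on size.** Grade II or higher acute GVHD by series:

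- primary immune deficiency: 7 + 1 = 8 of 37 (21.6%)
- mixed malignant and non-malignant: 4 + 6 = 10 of 41 (24.4%)
- AML: 14 of 33 (42.4%)
- non-malignant: between 0 and 3 of 23, because the table pools grades 1 and 2
- ALL and AML: between 0 and 24 of 80, for the same reason

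Denominator: 23 + 37 + 41 + 33 + 80 = 214.

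Lower count: 8 + 10 + 14 = 32, and 32/214 = 15.0%.

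Upper count: 32 + 3 + 24 = 59, and 59/214 = 27.6%.

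For grade II or higher acute GVHD, overstatement = rate × share of those patients alive and GVHD-free at 1 year. The share is not in the documents. Table 1 lists 0 + 1 + 9 + 10 + 4 = 24 chronic GVHD patients, but not how many also had acute GVHD or were still affected at 1 year. Its survival figures are at 2 or 5 years or by remission status, never at 1 year. The share can be anything from 0 to 1, so 15.0 and 27.6 points are ceilings for this component under the two counts, with a floor of zero.

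**The case against.** The best defence is the endpoint's name. Survival at a stated time is normally cumulative, and the documents use it that way for Day +100 event-free survival and for the 2-year figures in Table 1. On this view the incidence wording in the neighbouring entries is simply what incidence endpoints get, and events by 1 year were meant. This is plausible, and the status reading should not be presented as the authors' proven intention. But the one defining sentence and the data-collection sentence in section VII.1 both use status wording, and nothing elsewhere overrides them.

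Three further objections largely stand.

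- Early resolved acute GVHD is not hidden from the study's results. Grades II-IV and III-IV are reported at Day +100, and chronic GVHD as a 1-year cumulative incidence. A reader might infer that resolved GVHD goes unreported, but the documents support this only for acute GVHD that starts after Day +100 and resolves before 1 year.
- A reader might also infer that onset dates and grades will not be captured. Section V says that incidence and severity of acute GVHD will be collected, with no day limit, and the observation schedule is redacted, so no such gap can be claimed.
- The missing grade threshold can be read as any grade. It is missing detail, not an error. The estimator matters only with censoring, since Kaplan-Meier equals the simple proportion when follow-up to 1 year is complete.

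**Conclusion.** The point holds as a minor one. Followed as written, the rule scores resolved acute or chronic GVHD as GVHD-free and so overstates 1-year GVHD-free survival. It rests on taking the wording literally; if events by 1 year were intended, the text needs to say so. The endpoint is secondary and descriptive, with no target, test or stopping role, and the primary objective and the stopping rule do not depend on it.

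No size can be given. A reader might put a guessed share into the formula and quote a figure, for example 27.6% × 0.9 = 24.8 points. The documents do not support that. It treats every patient in the pooled grade 1-2 category as grade II. In addition, 14 + 24 = 38 of the 59 patients come from series with overall survival of 68% at 2 years and 72% at 5 years. Those are later time points, but they lend no weight to 90% alive and GVHD-free at 1 year. Table 1 also mixes donors, diseases and prophylaxis, so even its rates are only a guide for this trial.

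**What to change.** - **Section V.** Replace the sentence with: GVHD-free survival is the time from HSCT to the first of acute GVHD (of the grade the sponsor fixes before analysis), chronic GVHD, or death, estimated at 1 year by Kaplan-Meier with a 95% CI, with patients lost to follow-up censored. Grades II-IV would match the Abstract, but the threshold is the sponsor's choice.
- **Section VII.1.** Change the data item to any acute or chronic GVHD through 1 year, with onset date and maximum grade.
- **Optional.** Report GVHD prevalence at 1 year as a separate, clearly labelled result.
- **While editing.** Say how patients who leave the study early enter this endpoint, since section VI lists "Receipt of a second stem cell product" as an off-study criterion. This is missing detail and not part of the error.

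The cost is a few sentences and possibly some chart abstraction of GVHD dates and grades. No patients or visits are added. The estimate will usually be less favourable than under the status rule. If any-grade GVHD by 1 year was intended all along, a II-IV threshold would make it more favourable, which is why the grade must be fixed before the data are analysed.

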Patients attending the CCHMC bone marrow transplant (BMT) clinic who meet the eligibility criteria will be offered the opportunity to participate in this research study. The study is open to all participants regardless of gender or ethnicity.

2a. Inclusion Criteria

Any patient requiring an allogeneic HSCT who lacks an HLA-genotypically matched related donor. Genotypically matched related donors are allowed when there is a clinical desire to avoid the use of GVHD prophylaxis medications.

2b. Exclusion Criteria

Prior allogeneic transplant with active acute or chronic GVHD, or life-threatening infection. Patients with a prior history of allogenic transplant without active GVHD or life-threatening infection can be considered.

2c. Patients Requiring Second Allogeneic HCT or Additional Aliquots of Stored Hematopoietic Stem Cell Product

Patients may receive additional TCRA/b CD19 depleted product(s) if clinically indicated.

3. Randomization

Not applicable.

4. Procedures

Pre-Infusion Patient Evaluation:

Patients enrolled on this protocol will undergo evaluation for disease status and organ function per institutional HSCT guidelines prior to starting conditioning regimen.

Donor Selection:

Transplant donors will be selected based on institutional guidelines/SOPs.

Treatment Plan:

[REDACTED]

[REDACTED]

Informed Consent:

Informed consent will be obtained for each study participant (stem cell transplant recipient) and/or parent or legal guardian as appropriate. The study will be explained to the study subject in lay terms, in their native language. The informed consent process will require written consent by the patient (if ≥ 18 yrs of age) or parent/legal guardian.

The investigator will be available to answer any questions that the patient or caregiver may have regarding procedures, risks and alternatives. The signed consent form will be maintained in the study subject's chart with a copy being placed in the patient's medical record.

Preparative therapy:

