than 95% donor-derived cells but more than 5% donor-derived cells on a first and second confirmatory engraftment study (if the second study shows $\geq 95\%$ donor cells, the patient will be classified as having donor-derived hematopoietic cell recovery). Recipient-derived hematopoietic cell recovery will be defined as having 5% or less donor-derived cells. Any patient who fails to achieve neutrophil recovery within 42 days of allogeneic HSCT, or has 5% or less donor-derived cells will be considered as having primary graft failure. We will report the cumulative incidence of achieving initial donor-derived hematopoietic cell recovery. Complete blood counts and whole blood donor chimerism studies are frequently performed on a clinical basis following allogeneic HSCT. Stable hematopoietic cell recovery at 100 Days (+/- 2 weeks) will be defined as having hemoglobin, neutrophil, and platelet counts of at least 80% of the normal range in the absence of transfusions or clinical diagnoses which may affect the counts such as hemolytic anemia, auto-immune thrombocytopenia, iron deficiency, infection or medication induced bone marrow suppression, or other clinically relevant diagnosis. Patients with these or other medical diagnoses may still be considered to have count recovery. The percentage of donor cells will be recorded at Day +100 (preferably +/- 2 weeks) and Day +100 Donor-derived hematopoietic cell recovery will be defined as having 95% or greater donor-derived cells. Day +100 mixed donor and recipient-derived hematopoietic cell recovery will be defined as having less than 95% donor-derived cells but more than 5% donor-derived cells. Recipient-derived Day +100 hematopoietic cell recovery will be defined as having 5% or less donor-derived cells. These patients will be considered as having secondary graft failure. We will report rates of successful donor-derived hematopoietic cell recovery at Day +100. Exceptions may be made for patients with Severe Combined Immune Deficiency who may reconstitute with donor-derived T cells but have autologous recovery of myeloid and other cells. For such cases we will examine results of sorted T cell chimerism studies. We will also record the incidence of any additional cell product administrations or second allogeneic HSCT. Any patient who receives a second allogeneic HSCT will be considered as having graft failure.

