higher will be recorded on case report forms. Because the primary aim of this study is to assess safety of the infusion of TCR $\alpha\beta$ +/CD19+ depleted HSCT, and infusion reactions or other adverse events are expected to occur within 48 hours of the initial product infusion, we will only monitor and record AEs for the first week of the study. Any “attributable” events noted after this first week will be recorded and reported according to applicable institutional and federal regulations. Patients will be followed through Day +100 for endpoints including engraftment, acute GVHD, and event-free survival.

Expected events are those that have been previously identified as resulting from administration of the protocol therapy, those that can be attributed to the underlying condition, and/or those associated with transplant. An adverse event is considered unexpected, for reporting purposes only, when either the type of event or the severity of the event is not listed in the protocol and/or investigational brochure.

Please note that for the purpose of this study we will exclude the report of hematologic toxicities, as these subjects, by virtue of their underlying disease and/or condition and the transplant regimen, will develop hematologic abnormalities that otherwise would qualify as toxicity. Hematologic toxicities which are attributable to the underlying hematological disease and/or HCT preparative regimen will not be considered adverse events. In the event that any of these known complications of transplant or hematologic toxicities are thought to be at least possibly attributable to the study, the event will be recorded and subsequently reported to the IRB and FDA according to current reporting requirements.

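### In the legible text, the off-study criterion for a second stem cell product conflicts with following all patients to Day +100 and 1 year, so survival and GVHD data may be cut short at an outcome-related event

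*Combined protocol and SAP*

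**What the plan says.** Section VI keeps two lists. The one for removal from protocol therapy contains only patient withdrawal. The off-study list contains death, "Receipt of a second stem cell product" and loss to follow-up. For withdrawal of consent the section says what ends: the subject is "removed from further treatment and/or study observation immediately upon the date of request", with safety follow-up for at least one week after infusion. It gives no such explanation for a second product.

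Section VII.1 states that "All patients will be followed for primary and secondary endpoints for at least 100 Days following allogeneic HSCT" and that "1 year data will be collected regarding survival and presence or absence of acute or chronic GVHD". Section X.8 repeats the first part: "Patients will be followed through Day +100 for endpoints including engraftment, acute GVHD, and event-free survival". None of these makes an exception for patients given a second product.

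Section IV.2c, which covers both a second transplant and additional stored aliquots, says "Patients may receive additional TCRA/b CD19 depleted product(s) if clinically indicated".

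Section V treats these events as outcomes. Day +100 event-free survival counts as an event the receipt of an additional hematopoietic cell "product other than for control of infection (Donor lymphocyte infusion or Virus-Specific T cell infusion), and second allogeneic HSCT". On engraftment it says: "Any patient who receives a second allogeneic HSCT will be considered as having graft failure". Section VII.2 plans Kaplan-Meier curves for overall and event-free survival and names death as the competing event for the cumulative incidence curves.

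**The concern.** Leaving the study, listed next to death and loss to follow-up and apart from leaving therapy, most naturally means that observation ends. Sections VII.1 and X.8 say that observation goes on. No legible sentence says which prevails.

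The point matters because a second product is not a neutral event. It often marks failure of the first graft, and the protocol itself scores it as an event or as graft failure. If data collection stops there:

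- Kaplan-Meier overall survival treats these patients as if their later mortality were that of the patients still under observation.
- GVHD-free survival at 1 year, which rests on status at that time, has no status for them.
- The handling of a second graft in the GVHD incidence analyses is open, since only death is named as competing.
- A TRM death after the second product, but within 100 days of the first transplant, could go uncounted while the patient remains in the enrolled count of the stopping rule.

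**Working it through.** **The text.** The conflict needs no arithmetic. Section VI ends study participation at a second product; VII.1 and X.8 cover all patients without exception; no order of precedence is given. A second ambiguity lies beneath it: IV.2c allows both a second transplant and stored aliquots, and VI does not say whether an aliquot is a second stem cell product.

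**Share of patients affected.** The documents give no rate of second products. As an assumed proxy I use graft failure in Table 1, leaving out the AML study, whose cell is blank:

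- non-malignant disorders 4/23 (17.4%)
- primary immune deficiency 10/37 (27.0%)
- mixed indications 5/41 (12.2%)
- acute leukemia 2/80 (2.5%)
- pooled 21/181 = 11.6%
- pooled without the 2 + 8 labelled secondary: 11/181 = 6.1%

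**Overall survival.** Let f be the share of all patients who receive a second product, at a common time t0; S(t0) the survival of the others to t0; c their survival from t0 to 1 year; and g the same for second-product patients.

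- Kaplan-Meier, censoring at t0: [f + (1 − f)S(t0)] × c
- True: f × g + (1 − f)S(t0) × c
- Overestimate: f × (c − g)

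With c = 85% and g = 70% or 50%, all assumed:

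| f | g = 70% | g = 50% |
|---|---|---|
| 2.5% | 0.4 points | 0.9 points |
| 6.1% | 0.9 points | 2.1 points |
| 11.6% | 1.7 points | 4.1 points |

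The overestimate is zero if g = c. It is proportional to f, so the highest single-study rate, 27.0%, would give 4.1 or 9.5 points.

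**1-year GVHD-free survival.** At the pooled rate, 0.116 × 80 ≈ 9 patients have unknown status if nothing is collected (2 to 22 across the individual study rates). Best-case and worst-case values then differ by f, or 11.6 points at the pooled rate.

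**TRM stopping rule.** The plan states a type I error of 0.05 at TRM 30% and power above 80% at TRM 15%. Exact recursion over all 64 rows of Appendix 2 gives 0.012 and 62.3% as written, or 0.032 and 81.6% if stopping requires exceeding the listed number. Neither reading returns 0.05. That is a separate matter, but it means 0.05 is not a usable yardstick here, so I report only the change in the probability of never stopping at true TRM 30%.

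I take f = 6.1%, because the protocol classifies secondary failure at about Day +100, so products given for it would mostly come too late to matter for this window (an assumption). With q the TRM among second-product patients and every such death missed, observed TRM is 0.30 − f × q:

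| q | Observed TRM | As written (baseline 0.012) | If exceeding is required (baseline 0.032) |
|---|---|---|---|
| 30% | 0.282 | 0.026 | 0.062 |
| 50% | 0.270 | 0.041 | 0.093 |

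This corresponds to 0.061 × 0.30 × 73 = 1.3 or 0.061 × 0.50 × 73 = 2.2 missed deaths, out of 0.30 × 73 = 21.9 expected in 73 patients. If review catches half of them, the as-written values are 0.018 and 0.023.

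**The case against.** The best defence is that the passages can be read together. The off-study criterion contains no instruction to stop observing; where the protocol wants observation to end, at withdrawal of consent, it says so. VII.1 covers all patients, and the TRM rule counts deaths within 100 days without excluding retreated patients. A team that carries on with follow-up breaches nothing written. This stands as a reason to prefer continued follow-up, but it leaves the criterion with no defined effect, and a team could still apply it as worded.

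The redaction also counts. The required observations and post-transplant text in Section IV are blacked out and may hold a follow-up rule. A reader might infer that the plan definitely discards these data, or nowhere defines off study. The documents support only the narrower statement about the legible text.

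A reader might also infer that IV.2c contradicts Section VI. It does not: permission to receive another product is compatible with then going off study. What is missing is a statement of which products trigger the criterion.

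On size, overall survival is an analysis rather than a listed objective or secondary endpoint, and the reporting is descriptive and single-arm. The 4.1-point illustration is below one binomial standard error at n = 80: √(0.81 × 0.19/80) = 4.4 points. Graft failure is only a proxy for a second product, and a single centre may hold the later records anyway. All of this stands and limits the weight of the figures. It does not remove the bias, which has a consistent direction if retreated patients die more often, and which does not shrink with sample size.

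**Conclusion.** The concern holds in limited form. In the legible text the off-study criterion and the follow-up commitments conflict, and neither off study nor a second stem cell product is defined. Loss of data is a risk of the literal reading, not a demonstrated fact.

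Under that reading, 1-year overall survival is overestimated by f × (c − g), about 0.4 to 4 points for the illustrated shares of 2.5% to 11.6% and deficits of 15 or 35 points, and not at all without a deficit. 1-year GVHD status would be missing for about 9 of 80 patients at the pooled proxy rate. Share, timing and later survival are all assumptions.

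Day +100 event-free survival and graft failure already count these cases, and infusion safety of the first product is settled by then.

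A reader might infer that missed deaths push the stopping rule past its stated 0.05. The documents do not support that comparison, because the Appendix 2 boundary does not reproduce the figure. The effect is probably modest: the rule does not exclude retreated patients, TRM is reviewed about quarterly, and the medical monitor reviews protocol-associated deaths. The point should be fixed, with medium confidence in its practical weight.

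**What to change.** Reconcile Section VI with VII.1 and X.8 as a matter of data collection only:

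- Define off study, and state that after a second product all patients remain in follow-up for TRM to Day +100 from the first transplant, and for survival and GVHD to 1 year, unless consent is withdrawn.
- State what counts as a second stem cell product for this criterion, and in particular whether an additional stored aliquot under IV.2c does.
- Keep the second product or second transplant as an event-free-survival or graft-failure event, dated when it occurs, as Section V already defines.
- Prespecify for each GVHD endpoint how a second graft is handled, for example as a competing event or by ignoring it.

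The cost is a protocol amendment and chart follow-up of a few patients: about 9 of 80 at the pooled proxy rate, or about 5 (0.061 × 80) without the labelled secondary failures. Reported overall survival and TRM may look slightly less favourable. No treatment rule or sample size changes.

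### A patient given a second stem cell product before GVHD goes off study but is not a competing event, so the first-graft GVHD incidence would be modestly overstated

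*Combined protocol and SAP*

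**What the plan says.** - **Analysis (Section VII.2).** "Cumulative incidence curves will be created to analyze engraftment and acute GVHD". The next sentence adds: "Death will be treated as a competing event". No other competing event is named, no censoring rule is given, and chronic GVHD is not mentioned there.
- **Endpoints (Section V).** "We will report the cumulative incidence of achieving initial donor-derived hematopoietic cell recovery". For acute GVHD: "We will report the Day +100 cumulative incidences of acute GVHD grades II-IV and III-IV". Chronic GVHD is to be reported as a 1-year cumulative incidence.
- **Off study (Section VI).** The three criteria are death, loss to follow-up and "Receipt of a second stem cell product". Graft failure on its own is not among them.
- **Graft failure (Section V, Engraftment).** Primary failure covers "Any patient who fails to achieve neutrophil recovery within 42 days of allogeneic HSCT, or has 5% or less donor-derived cells". In addition, "Any patient who receives a second allogeneic HSCT will be considered as having graft failure".
- **Further products (Section IV.2c).** These are allowed when clinically indicated.
- **Follow-up (Section VII.1).** "All patients will be followed for primary and secondary endpoints for at least 100 Days following allogeneic HSCT". Survival and GVHD status are also to be collected at 1 year.

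**The concern.** A cumulative incidence estimator has three places for a patient at a given time: event, competing event, or censored. A patient who leaves the study alive and free of GVHD at a second product has had neither the event nor the only named competing event, so the default is censoring. Censoring assumes that the patient keeps the same later chance of first-graft GVHD as those still followed. That is not credible for someone re-transplanted because the first graft was lost.

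The plan already counts graft failure, additional products (with exceptions for infection control) and second HSCT as events in Day +100 event-free survival, but leaves them out here. Limiting acute GVHD is part of the study hypothesis, so an artefact that raises GVHD works against the product's own case. The affected results are secondary and descriptive.

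**Working it through.** The plan states no expected GVHD or engraftment figure, so there is none to reproduce.

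**Inputs from Table 1**
- Graft failure, four series reporting it: 2/80 (2.5%), 5/41 (12.2%), 4/23 (17.4%), 10/37 (27.0%). Pooled: (2 + 5 + 4 + 10)/(80 + 41 + 23 + 37) = 21/181 = 11.6%.
- Chronic GVHD, five series: (0 + 1 + 9 + 10 + 4)/(23 + 37 + 41 + 33 + 80) = 24/214 = 11.2%.
- Latest neutrophil engraftment in any stated range: day 28 (one series gives no range).

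**Assumptions not in the documents**
- Failure on days 20–42. Every failure leads to a second product 14 days later, on days 34–56 (mean 45). No first-graft GVHD after failure.
- Acute GVHD: 20% or 30% in an intact graft, spread evenly over days 15–100; 10% deaths by day 100.
- Chronic GVHD: spread evenly over days 100–365; 20% deaths by 1 year.

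**Step 1: graft failure without a second product.** With complete follow-up the estimator is the number with GVHD divided by all patients. A patient who can no longer have first-graft GVHD adds 0 to the numerator and 1 to the denominator, whether kept in the risk set or coded as a competing event. The shift is 0, and simulation confirms this.

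**Step 2: size of the shift when censored at the second product.** Censoring credits each such patient with the later GVHD risk of intact grafts:

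shift ≈ g × q × (share of onset after the second product) × (average survival over that span),

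where g is the proportion with graft failure and q is GVHD in an intact graft.

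*Acute.* Share = (100 − 45)/(100 − 15) = 0.647. Survival at the midpoint, day 72.5, is 1 − 0.10 × 0.725 = 0.93. The product is 0.60.

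| g | q | Formula | Simulated, censored vs competing (400,000 patients) |
|---|---|---|---|
| 2.5% | 20% | 0.3 points | – |
| 2.5% | 30% | 0.45 points | – |
| 11.6% | 20% | 1.4 points | 18.5 vs 17.1% |
| 11.6% | 30% | 2.1 points | 27.8 vs 25.6% |
| 27% | 20% | 3.2 points | 18.0 vs 14.7% |
| 27% | 30% | 4.9 points | 27.2 vs 22.1% |

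*Chronic.* All second products precede day 100, so the share is 1. Survival at the midpoint, day 232.5, is 1 − 0.20 × 232.5/365 = 0.873.
- Pooled rates: 0.116 × 0.112 × 0.873 = 1.1 points.
- The 41-patient series: 0.122 × (9/41) × 0.873 = 2.3 points.
- The immune-deficiency series: 0.27 × (1/37) × 0.873 = 0.6 points.
- With q = 30%: 3.0 points at g = 11.6% (simulated 26.1 vs 23.1%) and 7.1 at g = 27% (26.2 vs 19.1%).

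**Step 3: are the large shifts realistic?** The series with 27% graft failure had chronic GVHD in 1/37, not 30%. The one series with about 30% chronic GVHD (10/33) does not report graft failure. For acute GVHD, the 27% series had grades II–IV in 8/37 (21.6%), but 8 of its 10 failures are listed as secondary and their timing is not given. Primary failures only: (2/37) × (8/37) × 0.60 = 0.7 points. All ten early: 0.27 × 0.216 × 0.60 = 3.5 points.

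**Step 4: engraftment.** Second products on days 34–56 come after day 28, so censoring changes nothing: 0 points. If they came on days 18–35, with engraftment spread over days 9–28, the overstatement would be 1.3 points at 2.5% failure and 8.0 points at 27%.

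**Step 5: other assumptions.** With 80 patients, second products at graft loss on days 25–60 for acute GVHD (25–180 for chronic), acute GVHD 10–30% and chronic GVHD 5–25%, shifts across 2.5–27% graft failure were 0.2–4.8 points (acute) and 0.1–5.6 points (chronic). If only half of failures receive a second product, the 1.4-point acute shift falls to 0.7.

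**The case against.** **Censoring is inferred, not stated.** No section gives a censoring rule, and Section VII.1 promises at least 100 days of follow-up for everyone. The post-HSCT observation schedule is blacked out and may cover follow-up after a second product. This stands as a limit on certainty. It does not remove the point, because Sections VI and VII.1 disagree and Section VII.2 does not settle it.

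**A reader might infer that all patients with graft failure are censored.** The documents do not support that. Graft failure is not an off-study criterion, and such patients cause no bias while they are followed.

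**A reader might infer that engraftment is also biased upward.** That is not automatic. It requires second products before the last first-graft engraftment, whereas the timing assumed above gives zero. Table 1's neutrophil days are only a proxy for donor-derived recovery.

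**A reader might want graft failure itself made a competing event.** The definition of primary failure includes slow neutrophil recovery without regard to chimerism. A patient with slow counts but donor cells meets it and can still develop GVHD, which such a rule would discard.

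**The direction depends on the target.** If GVHD after a second graft is meant to count, censoring could bias downward instead. The plan does not say which is intended, and Section IV.2c allows further products. This stands and is a reason to state the target.

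**Conclusion.** The point holds in a limited form. If the off-study rule ends follow-up at a second product, patients re-treated before GVHD are censored informatively and first-graft GVHD is overstated. Under the stated assumptions the shift is about 0.3 to 2 points for Day +100 acute GVHD at 2.5% to 11.6% graft failure, and about 1 point for 1-year chronic GVHD at pooled Table 1 rates. In 80 patients, 2 points is 80 × 0.02 = 1.6 patients. All of these figures assume that every failure leads to a second product, so they lean high.

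A reader might take 3 to 7 points as the expected bias. Reaching it takes 27% early graft failure with high latent GVHD or, at the 3-point end for chronic GVHD, 30% latent incidence at the pooled failure rate. Table 1 does not show either combination within one series.

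The amendment is still worthwhile: the effect is modest and on secondary endpoints, but it is avoidable at little cost before analysis.

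**What to change.** In Section VII.2 write: *For acute and chronic GVHD, death and second allogeneic HSCT before GVHD are competing events; for initial donor-derived recovery, death and second allogeneic HSCT before recovery are competing events.* Then:

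- Do not make graft failure alone a terminal event.
- Report GVHD after a second graft descriptively.
- State how additional aliquots that are not a second HSCT are handled, because the off-study criterion in Section VI is wider than second HSCT.
- Reconcile that criterion with the 100-day and 1-year follow-up in Section VII.1.

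**Cost.** Mainly wording: Section V already has additional products and second HSCT recorded, and their dates will be needed. The estimates will describe the first graft only, and the engraftment figure may be lower if any second product is given early.
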